## 6.2 Method of Assignment/Randomization (if applicable)

N/A

## 6.3 Adverse Events Definition and Reporting

This is an observational study with minimal risk, we do not anticipate any untoward events occurring in association with the study.

Adverse events (AEs) will be evaluated retrospectively via chart review. If AEs are identified, they will be reported to the Principal Investigator and PI will notify the IMPACT Collaboratory. Subsequently IMPACT Collaboratory will notify the National Institute of Aging, the Data and Safety Monitoring Board and the Advarra IRB within 48 hours of AE notification. If an adverse event is unexpected, the PI will determine if the event places the participant or others at greater risk of physical or psychological harm than previously known. The PI will report any potential harm to IMPACT Collaboratory who will then report this to the NIA and the IRB within 2 weeks of the event.

#### **6.4 Reaction Management**

N/A

#### **6.5 Withdrawal Procedures**

Study participant's consent to participate will be verified during every encounter with research staff. Participants can verbally report their withdrawal from the study.

### **7 Statistical Design**

This is an observational pilot study and descriptive statistics will be completed comparing demographic and clinical characteristics of all patients 65+ discharged from the ED (denominator) versus those referred from the ED for outpatient cognitive impairment assessment. Student's t-test will be used for continuous variables (if normally distributed (e.g. age)) or the Wilcoxon rank-sum test (if not normally distributed (e.g., length of stay)), and the Chi-square test or Fisher's exact test for binary/categorical variables. All tests will be 2-sided at a significance level of 5%.

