#### **4.2 Outcome Variables/Endpoints**

As this is a feasibility study, we are not testing hypotheses. Observational results gathered from this study will inform effect sizes needed to propose a future full-scale, pragmatic, multicenter study.

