#### **Standard Care for Outpatient Cognitive Assessment Referral**

The outpatient clinics receiving the ED referrals will reach out to patients to establish and schedule an outpatient evaluation after discharge from the ED.

As part of routine care, the outpatient assessments may include brief neuropsychological tests of cognition memory, language, executive function and attention that may include the Montreal Cognitive Assessment (MoCA), a cognitive screening test to aid in detecting cognitive impairment and evaluations to assess competency in completing instrumental activities of daily living such management of money, behavioral deficiencies and others for standardized consensus evaluation for diagnosis of dementia, cognitive impairment or normal with subtype of impairment. The outpatient evaluations will allow for clinical diagnosis and validation of ED assessment for the presence of dementia or mild cognitive impairment.

In addition, following the evaluation, the outpatient centers will document cognitive impairment diagnoses (if present) and notify patients, caregivers and their primary care providers of results. The centers will utilize available resources to connect patients to their primary care provider with feedback and recommendations for brain health care and management.

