#### **7.1 Sample Size Considerations**

This is a feasibility study. Results gathered here will inform future sample, effect, and power calculations.

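### Section 7 tests referred patients against a group that contains them, so the named independent-sample tests do not hold their stated 5% level and, through the overlap, give p-values that are too large

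*Combined protocol and SAP*

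**What the plan says.** Section 7 (Statistical Design) announces descriptive statistics "comparing demographic and clinical characteristics of all patients 65+ discharged from the ED (denominator) versus those referred from the ED" for outpatient cognitive assessment. It then assigns a test to each type of variable:

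- "Student's t-test will be used for continuous variables (if normally distributed (e.g. age"), for continuous variables judged normal;
- "the Wilcoxon rank-sum test (if not normally distributed (e.g., length of stay"), for the other continuous variables;
- "the Chi-square test or Fisher's exact test for binary/categorical variables".

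It closes with "All tests will be 2-sided at a significance level of 5" percent.

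Other sections place the referred patients inside the first group. Section 5.3 makes discharge from one of the two EDs an inclusion criterion. Section 6.1, on standard care after referral, says that the receiving clinics "will reach out to patients to establish and schedule an outpatient evaluation after discharge from the ED". No section defines a not-referred comparator, and none names a one-sample or overlap-adjusted test.

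Two statements limit the weight of the comparison. Section 4.2 says "As this is a feasibility study, we are not testing hypotheses". Section 7.1 gives no power basis and says only "Results gathered here will inform future sample, effect, and power calculations".

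**The concern.** All four named tests assume that the two groups share no patients. Calling the first group the denominator, and including everyone discharged, makes it the whole from which the referred patients are drawn. An analyst who follows the text enters each referred patient twice.

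The resulting difference, referred minus all, is a legitimate description of how referred patients differ from their source population. The p-value attached to it is not valid. The two means are positively correlated, the tests ignore this, and the standard error comes out too large. Real differences in who gets referred may then be reported as not significant. This is the comparison that Section 7 states together with its tests, and Section 7.1 says that the results will feed the design of the later trial.

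**Working it through.** **Inputs.** The two-sided 5% level, the tests and the groups come from Section 7. The documents give neither the number of discharges aged 65 or over (N) nor the referred fraction (f), so f is an assumption and a range is shown. The 80% power used below is also an assumption, because Section 7.1 sets none.

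**Plan's own figure.** With separate groups the level is 2Φ(-1.96) = 0.0500. The stated 5% is therefore reproduced for referred versus not referred, but not for the groups that Section 7 describes.

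**Derivation.** Let n = fN be the number referred, s the common standard deviation, and D the difference between referred and not referred.

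- Observed difference, referred minus all: (1-f)D.
- Standard error used by an independent-samples test: s·sqrt(1/n + 1/N) = s·sqrt((1+f)/(Nf)).
- True standard error of that difference under the null: s·sqrt(1/n - 1/N) = s·sqrt((1-f)/(Nf)).
- Standard error of D with separate groups: s·sqrt(1/(Nf(1-f))).

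Hence z(planned) = k·z(separate), with k = sqrt((1-f)/(1+f)). At f = 10%, k = sqrt(0.90/1.10) = 0.905.

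**Results.**

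- True level = 2Φ(-1.96/k).
- Reported p where separate groups give 0.050 = 2Φ(-1.96k).
- Power where separate groups have 80% = Φ(2.80 - 1.96/k).
- Detectable-difference ratio at 80% power = (1.96/k + 0.84)/2.80.

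| f (assumed) | k | True level | Reported p for 0.050 | Power for 80% | Increase in detectable difference |
|---|---|---|---|---|---|
| 1% | 0.990 | 4.8% | 0.052 | 79% | 0.7% |
| 5% | 0.951 | 3.9% | 0.062 | 77% | 3.6% |
| 10% | 0.905 | 3.0% | 0.076 | 74% | 7.4% |
| 20% | 0.816 | 1.6% | 0.110 | 66% | 15.7% |

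At f = 2% the true level is 4.55%. At f = 10% a separate-groups p of 0.030 becomes 0.0497, so any result between 0.030 and 0.050 crosses to not significant.

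**Simulation under the null** (N = 2,000 assumed; rejection rates at f = 5%, 10%, 20%):

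| Test | Groups as planned | Separate groups |
|---|---|---|
| t-test | 3.7, 3.1, 1.6% | 4.8, 5.1, 5.1% |
| Wilcoxon, skewed data | 4.0, 3.0, 1.6% | 5.1, 5.1, 4.9% |
| Chi-square, 40% prevalence (assumed) | 3.9, 3.0, 1.6% | 5.0, 5.0, 5.0% |
| Fisher, 5% prevalence (assumed) | 2.6, 2.4, 1.5% | 3.6, 3.9, 4.4% |

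The first three tests follow the formula. Fisher's test is already conservative with separate groups, and the overlap lowers its level further.

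**The case against.** **Conservative only under equal spread.** If referred patients are more variable than the rest, the pooled t-test can exceed 5% even with overlap. At f = 5% and a variance ratio of 1.5, its level is 8.3% with overlapping groups and 10.2% with separate groups. This stands as a qualifier: nobody can promise that the planned t-test stays below 5% in every case. But it is a separate pooled-variance problem, and the overlap still lowers the level in every case computed.

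**The size depends on an unknown.** Referral is at the physician's discretion and limited to suspected impairment without documented dementia, while the denominator is every discharge aged 65 or over from two EDs. A small f is plausible, and at 1-2% the effect is negligible. That is fair, and the 10% and 20% rows are illustrations. Still, the referral rate is itself an outcome (Section 4.2.1), so the validity of the test should not depend on it.

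**Nesting may be partial.** Section 5.1 defines the population by referral without mentioning discharge, and the data table in Section 6.1.1 records disposition as discharged or admitted. Any admitted referrals would reduce the overlap, but the groups would still not be separate.

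**Loose wording.** The authors may mean referred versus not referred, which is what a two-group test by referral status gives with one record per patient. If so, saying it costs nothing; the text as it stands points the other way. The sentence on tests may also be meant for the site and subgroup comparisons, but that does not remove it from this one.

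**Little depends on it.** The comparison is descriptive and no hypotheses are tested. This is accepted and sets the severity. A plan that prescribes p-values at a stated level should nevertheless prescribe valid ones.

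**Conclusion.** The concern holds and is minor. As written, Section 7 applies independent-sample tests to a whole and its own part, and the 5% level is not attained for any f above zero. The overlap acts conservatively, from trivial at 1-2% referred to a true level of 3.0% at 10% and 1.6% at 20%. These figures assume full nesting, equal spread in referred and not-referred patients, and the stated values of f. The primary rates and the descriptive referred-minus-all difference are unaffected; only the p-values are wrong.

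**What to change.** Replace the comparison in Section 7 with wording such as: *The named tests will compare discharged patients aged 65 or over who were referred with those who were not referred (mutually exclusive groups). All discharged patients aged 65 or over will be shown in a descriptive column without p-values.*

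Section 5.5 (all ED records against the enrolled population) and Section 7.3 (all eligible subjects against the subset of 100) also set a whole beside its part. They name no test and need no change. If p-values are reported there, compare enrolled with not enrolled in the same way.

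The cost is one or two sentences. The tests and the records are the same, and no new data are needed. The change does not address unequal variances in the pooled t-test, which is a separate choice.

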#### **5.3 Eligibility Criteria**

In order to be eligible for inclusion in the study, an individual must meet all of the following criteria:

- Adults age 65 or older
- Discharged from the adult ED at YNHH or the ED at NMH

Any individual who meets any of the following criteria will be excluded from participation in this study:

- Documented or known history of dementia
- Alcohol/substance intoxication while in the ED
- Non-English or Non-Spanish speaking

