## **5.5 Consent/Assent Procedures/HIPAA Authorization**

A partial waiver of HIPPA Authorization and waiver of written informed consent will be sought for recruitment and screening of patients in the ED. purposes A convenience sample of total of 100 eligible subjects will be contacted by telephone for follow-up and informed telephone assent with a waiver of written consent to participate in telephone surveys and medical record review. We will screen for basic inclusion and exclusion criteria via the electronic medical record (EMR). These waivers of HIPAA authorization and written informed consent for recruitment/screening purposes will lessen burden on patients and families (since we only intend to enroll patients who meet basic inclusion criteria), and still allow us to accurately report the number and characteristics of screened patients.

A full waiver of HIPPA Authorization is being sought for all the ED patient (EMR)records over 65 years of age during the study time period to compare with the enrolled population.

These waivers are being sought as the study is of minimal risk and for restrictions in place because of COVID.

Trained research staff will contact eligible participants by telephone approximately at 1-6 weeks and again at 3 months after their ED visit. The study will be explained to the potential participant, and any questions will be discussed. If the study personnel have concerns over the patient's capacity for informed decision making, the patient's capacity to consent will be assessed through performance of the University of California San Diego Brief Assessment of Capacity to Consent. If the patient is determined, based on a score of <10 on the capacity of assessment, to not able to make an informed decision, a proxy or legally authorized representative will be sought for consent. If the patient regains decision-making capacity during the course of the study (for example, if delirium was present at enrollment but subsequently resolves), then consent will be obtained from the patient. If the patient then refuses to consent or withdraws consent given by the proxy, the patient will be disenrolled from the study.

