## **6 Study Methods/Procedures**

### **6.1 Study Procedures**

#### **Clinical ED Practice Intervention.**

As part of routine ED care, clinicians conduct delirium screening at bedside to evaluate presence of cognitive impairment in ED who are 65 years and older. The intervention will augment this process to include questions assessing for documented history of dementia or asking the patient, or caregivers present, in the ED if the patient has had any memory or thinking problems in the past year. If clinicians suspect the patient may have cognitive impairment, regardless of the response from patient or caregiver, and the patient has no documented history of dementia, the physicians may refer these patients to available outpatient cognitive evaluation. Referral will occur using EMR outpatient consult requests or by emailing outpatient clinics for available appointments as part of routine patient care referral processes.

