#### **7.3 Data Relevance**

Data analyses will consist of descriptive statistics comparing overall eligible subjects at both sites and of the subset of 100 patients for which chart review will be completed.

A valid analysis of the intervention effect between gender and racial/ethnic subgroups will be completed to identify differences between the subgroups and their characteristics.

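### Section 7 compares referred patients with all discharged patients 65+, including those with documented dementia, who fall outside the referral step

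*Combined protocol and SAP*

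**What the plan says.** Section 7 sets out a descriptive comparison of "all patients 65+ discharged from the ED (denominator) versus those referred from the ED for outpatient cognitive impairment assessment". It uses t-tests or Wilcoxon tests for continuous variables and chi-square or Fisher tests for categorical ones, all two-sided at 5%. It names no exclusions.

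Section 6.1 (Clinical ED Practice Intervention) describes who enters the referral pathway. If impairment is suspected and "the patient has no documented history of dementia, the physicians may refer these patients" for outpatient evaluation.

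Section 5.3 includes "Adults age 65 or older" and "Discharged from the adult ED at YNHH or the ED at NMH". It then lists three kinds of patient who "will be excluded from participation in this study": those with "Documented or known history of dementia", those intoxicated in the ED, and those outside the language criterion.

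Two other places describe a comparison group. Section 5.5 seeks a waiver for "all the ED patient (EMR)records over 65 years of age during the study time period to compare with the enrolled population". Section 7.3 speaks of "comparing overall eligible subjects at both sites" and of the subset of 100 patients with chart review.

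Outcome bases appear elsewhere. Section 4.2.1 takes screening and detection rates over all older ED patients, and successful referral over those found to be at risk. The Synopsis lists a referral rate among screened patients.

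**The concern.** A comparison of referred patients with other ED patients should show whom clinicians pick out for cognitive evaluation. If the comparator includes people who could not have been picked, part of the contrast is fixed by rule and says nothing about how the intervention works. Patients with documented dementia are in that position. They also cannot be target cases, because the study looks for undiagnosed impairment.

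The same people enlarge the base that Section 7 labels the denominator. Sections 4.2, 7.1 and 7.2 say that the pilot's estimates will feed the planning of a larger trial. A referral yield per older discharged patient and a yield per patient who could be referred are different planning figures, and the plan does not say which one it will report.

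**Working it through.** There is no figure in the plan to reproduce. The documents give no referral rate, no dementia prevalence and no ED volume. The numerical values in steps 2 to 4 are therefore assumptions, except the 5% test level, which is from Section 7.

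**Step 1. Which rule affects which comparison.**

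| Rule | Source | Removes a patient from the referred group? | Removes a patient from the enrolled sample? |
|---|---|---|---|
| Documented dementia | 6.1 and 5.3 | Yes | Yes |
| Intoxication in the ED | 5.3 only | No | Yes |
| Language | 5.3 only | No | Yes |

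The Section 7 contrast (discharged versus referred) is affected by the first row only. The Section 5.5 contrast (all records versus enrolled) is affected by all three, because Section 5.3 governs enrolment.

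**Step 2. Effect on a referral rate.** Let r be the referral rate among discharged patients 65+ without documented dementia, and d the share of all discharged patients 65+ who have it. Then reported rate = r(1-d), and the relative understatement is d. With r = 10%:

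- d = 5%: 10% x 0.95 = 9.5%
- d = 10%: 10% x 0.90 = 9.0%
- d = 20%: 10% x 0.80 = 8.0%

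**Step 3. Effect on the test of dementia history.** Assume 5,000 discharged patients, with no documented dementia among the referred (by rule) and all 5,000 x d cases among the non-referred. Two-sided Fisher exact p-values:

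| Assumed d | Cases | 100 referred | 50 referred |
|---|---|---|---|
| 2% | 100 | 0.27 | 0.63 |
| 5% | 250 | 0.0095 | 0.18 |
| 10% | 500 | 0.00006 | 0.008 |

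With 1,000 discharged patients in place of 5,000 the results lead to the same conclusions. At d = 10%, or at d = 5% with 100 referred, the planned test would be significant at 5% through the referral rule alone. At d = 2% it would not.

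**Step 4. Knock-on effect on other characteristics.** If patients with dementia are D years older on average, the comparator mean age moves by d x D. With d = 10% and D = 5, the shift is 0.5 years. With SD 8 and 100 versus 5,000 patients, the power to detect that is about 9%. With d = 20% and D = 7, the shift is 1.4 years and the power about 41%. The indirect effect is thus small unless d and D are both large.

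**The case against.** The strongest reply is that an all-65+ base is deliberate. Section 4.2.1 measures screening and detection in all older ED patients, Section 5.2 has all of them screened, and the intervention itself includes asking about documented dementia. That stands for screening and detection, and nothing here should change those rates.

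A second reply is that the Section 7 sentence concerns patient characteristics and does not itself define a referral rate, while Section 4.2.1 and the Synopsis give other bases (at-risk and screened patients). This also stands in part: the understatement in step 2 arises only for a rate calculated on discharged patients. But Section 7 does call that group the denominator, and the comparison of characteristics is affected whichever rate is reported.

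A third reply is that Section 4.2 says no hypotheses are tested. The consequence is indeed one of interpretation and planning. Section 7 nevertheless specifies tests at 5%, and their p-values will be read.

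Some stronger readings are tempting but not supported:

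- A reader might infer that all three Section 5.3 exclusions bar referral. They bar study participation. Nothing in the documents stops an intoxicated patient, or one who speaks another language, from being referred, so a language difference between referred and other patients is not built in.
- A reader might infer that Section 7 uses the wrong age limit. It uses 65+, as Section 5.3 does. Only the waiver sentence in Section 5.5 says over 65. Because groups rather than age-matched individuals are compared, this is a boundary wording mismatch.
- A reader might take Sections 7 and 7.3 as a flat contradiction. They describe different contrasts. What is missing is a statement of whether the eligibility implied in 7.3 also applies to the comparators in 7 and 5.5.

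**Conclusion.** The point holds for documented dementia in the Section 7 comparison, and for all three exclusions in the Section 5.5 comparison with the enrolled sample. As written, the contrast between referred and other patients is partly built in by the referral rule. A referral rate on discharged patients is understated by the share d with documented dementia, which is one half to two percentage points on a 10% rate if d is 5% to 20%. Both the rate and the range of d are assumptions. The direct effect on dementia history can be large enough to be significant; the indirect effect on age is probably small. The plan should be corrected because its estimates are meant for trial planning. The matter concerns interpretation and does not touch patient safety.

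**What to change.** In Section 7, restrict the comparator for referred patients, and any referral rate based on discharged patients, to discharged patients 65+ without documented dementia. Report those with documented dementia as a separate count. Do not filter this group on intoxication or language: such patients can still be referred, so removing them from the denominator would leave them in the numerator. Keep all patients 65+ as the base for screening and detection, and name the base beside each rate.

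For the comparison with the enrolled sample (Section 5.5), apply to the comparator those Section 5.3 criteria that can be read from the EMR, in line with the eligible subjects of Section 7.3, and report the patients removed by reason. Align the age wording of the waiver with the 65-or-older criterion.

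The cost is a filter on EMR fields, since Section 5.5 already screens the inclusion and exclusion criteria through the EMR, plus a few sentences of text. The downside is that exclusions not coded in the EMR will be caught incompletely, which should be stated with the results.

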#### **3.2 Hypothesis**

We are evaluating the feasibility of implementing a quality improvement initiative of ED screening, referral, and care coordination process of older ED patients with UCID. We hypothesize this will be feasible.

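### Section 7 sets 5% significance tests, including Student's t-test, for comparisons that Section 4.2 says involve no hypothesis testing; estimates with Welch intervals and non-overlapping groups would serve better (minor)

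*Combined protocol and SAP*

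**What the plan says.** Section 4.2 (Outcome Variables/Endpoints) states: "As this is a feasibility study, we are not testing hypotheses". Section 3.2 does record a hypothesis, "We hypothesize this will be feasible", but attaches no numerical criterion to it.

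Section 7 (Statistical Design) begins: "This is an observational pilot study and descriptive statistics will be completed comparing demographic and clinical characteristics". The two groups are "all patients 65+ discharged from the ED (denominator) versus those referred from the ED for outpatient cognitive impairment assessment". A test is then assigned by type of variable. For continuous variables, Student's "t-test will be used for continuous variables (if normally distributed (e.g. age". Continuous variables that are not normal, with length of stay as the example, go to the Wilcoxon rank-sum test, and categorical variables go to chi-square or Fisher's exact test. The paragraph ends: "All tests will be 2-sided at a significance level of 5" per cent.

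Section 7.3 adds descriptive statistics "comparing overall eligible subjects at both sites and of the subset of 100 patients" and names no test for them. The plan gives no size for the referred or the discharged group, no SD and no list or count of the characteristics to be compared.

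**The concern.** A significance level has a function only if null hypotheses are being tested. With Sections 4.2 and 7 as they stand, an analyst cannot tell whether p-values belong in the report or how they should be read.

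The named t-test is also a weak choice for this comparison. Referred patients are likely to be a small part of the discharged population aged 65 or over. When variances are pooled, the larger group largely determines the standard error, so a different spread in the smaller group is hardly reflected. Referral follows clinicians' suspicion of cognitive impairment (Section 6.1), so there is no reason to take equal spread for granted.

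What is at stake is modest: how accurately the report describes the way referred patients differ from other discharged patients. Sections 4.2 and 7.1 say that the study exists to supply estimates for a later trial. A p-value gives neither the size of a difference nor its precision.

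**Working it through.** **The plan's own figure.** The 5% is a chosen level, not a derived one, so there is nothing to reproduce.

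**Inputs.** The two-sided 5% level and Student's t-test come from Section 7. Everything else is assumed: a small group of n = 100, a large group of N = 1,000 to 10,000, and a ratio r of the small group's SD to the large group's SD from 0.8 to 1.5. The figure of 100 is the enrolled sample in Section 5.2. It is borrowed as an illustrative size and is not stated to be the number referred.

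**Pooled t-test, separate groups.** Set the large group's SD to 1.

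- Pooled variance: sp² = [(n−1)r² + (N−1)] / (n+N−2)
- Standard error used by the test: √[sp²(1/n + 1/N)]
- True standard error: √(r²/n + 1/N)
- True level ≈ 2Φ(−1.96 × SE used / true SE)

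For n = 100, N = 10,000, r = 1.25: sp² = (99×1.5625 + 9,999)/10,098 = 1.0055. SE used = √(1.0055×0.0101) = 0.1008. True SE = √(0.015625 + 0.0001) = 0.1254. The ratio is 0.804, and 2Φ(−1.575) = 11.5%.

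For r = 0.8: sp² = 0.9965, SE used = 0.1003, true SE = √0.0065 = 0.0806. The ratio is 1.244, and 2Φ(−2.439) = 1.5%.

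Simulation with 100,000 runs per case agrees (true level at nominal 5%, pooled / Welch):

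| SD ratio r | 100 v 1,000 | 100 v 5,000 | 100 v 10,000 |
|---|---|---|---|
| 0.8 | 1.9% / 5.1% | 1.6% / 5.0% | 1.4% / 4.9% |
| 1.0 | 4.9% / 4.9% | 4.9% / 4.9% | 5.0% / 5.0% |
| 1.25 | 10.2% / 5.0% | 11.3% / 5.1% | 11.4% / 4.9% |
| 1.5 | 15.7% / 4.9% | 18.3% / 4.9% | 18.8% / 5.0% |

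With 100 against 100 the pooled test stays at 5.0% to 5.1% for every ratio tried. With r = 1 it stays near 5% at every size. The level therefore fails only when sizes and variances are both unequal.

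**Overlap.** As worded, the denominator contains the discharged patients who were referred. For a subset of n inside a whole of N with equal SDs, the variance of the difference in means is proportional to 1/n − 1/N. A two-sample test assumes 1/n + 1/N. The true level is 2Φ(−1.96√[(1/n + 1/N)/(1/n − 1/N)]). For n = 100 and N = 1,000 the ratio under the root is 0.011/0.009 = 1.222, which gives 3.0%. The same formula gives 4.6% at N = 5,000 and 1.6% at N = 500. Welch's test does not cure this, because it too assumes independent groups.

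**The case against.** The best defence is that the two sections speak of different things. Section 4.2 sits under endpoints, while Section 7 calls its comparisons descriptive, and a table of patient characteristics with p-values is not a test of an endpoint. The primary outcomes are rates of screening, detection and referral. No go/no-go rule uses these p-values. The t-test applies only to continuous variables judged normal, and age is the only example. The word pooled does not appear; it is inferred from the name of the test. No group sizes or SDs are given, and nothing in the documents points to a particular SD ratio. Most of this stands, and it is why the point is minor. It does not remove the conflict, because the 5% rule sits in the same paragraph as the descriptive label and nothing says how the p-values are to be read.

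A reader might infer more than the documents support:

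- **That chance differences will pass as findings for want of multiplicity control.** With 10 or 20 tests the chance of at least one false positive is 1 − 0.95^10 = 40% or 1 − 0.95^20 = 64%. Those figures need independent characteristics that are all truly null, and an assumed count. Patients are referred on suspected impairment, so some real differences are to be expected. Formal adjustment is not required for descriptive comparisons in a pilot.
- **That error rates are wrong for every characteristic.** The variance problem is confined to the t-test, and it can make the test conservative as well as liberal.
- **That the comparison with the 100 enrolled patients in Section 7.3 uses the same t-test.** That section names no test.

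**Conclusion.** The point holds as a minor one. Sections 4.2 and 7 need reconciling, and Student's t-test is a poorer choice than Welch's for the continuous variables it covers. The size given in the table is conditional: it assumes about 100 referred patients, a comparator of at least 1,000, variances pooled in the classical way, and SDs that differ. If the SDs are equal, or the groups are similar in size, no distortion arises from this source. The overlap is more certain, since it follows from the wording of Section 7 itself, although its effect is small when few of the discharged patients are referred. No endpoint or decision is put at risk. The change is worth making because it costs almost nothing and gives the future trial estimates in place of verdicts.

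**What to change.** 1. In Section 7, delete the sentence setting the 5% level and state that the comparisons are estimation, consistent with Section 4.2.
2. Define the groups as referred versus not-referred discharged patients aged 65 or over. The intervals below are not valid without this step.
3. Report each raw difference with a 95% interval: Welch for means, risk differences for categories, and a median-based summary with its interval for skewed variables such as length of stay.
4. If p-values are kept, use Welch's t-test in place of Student's, and label all of them exploratory and unadjusted for multiplicity.

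The cost is a few sentences in the statistical section. No new data are needed: the full waiver described in Section 5.5 is already sought for the records of older ED patients generally. The downside is that fewer results can be reported as significant.
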